The randomized HES and standard therapy groups will be descriptively compared for balance on potentially confounding baseline variables (including duration of cardiopulmonary bypass, use of anti-fibrinolytic therapy, preoperative anticoagulant medications, including clopidogrel). Any baseline variable for which the standardized difference (i.e., observed difference in means or proportions divided by the pooled standard deviation of the outcome) is greater than 0.25 will be considered imbalanced and adjusted for as a covariate in each of the below analyses. We will not use P-values to determine baseline imbalance since the P-value is quite dependent on the sample size, whereas the standardized difference is more independent of sample size and thus a better assessment of balance. [A standardized difference of 0.25 is conservative (should be 0.39) based on the expected 2.5th and 97.5th percentiles of the sampling distribution, i.e., $1.96 \times \sqrt{2/n}$ per group = 50 = 0.39.]³⁰ For all analyses of continuous variables, transformations of the data will be made as appropriate to achieve normality and/or meet other model assumptions. If transformations are not successful, non-parametric analyses analogous to those described below will be employed. For example, we might employ a Wilcoxon rank-sum test to compare the groups on IL-6 at a particular time point if the data are not close to a normal or log-normal distribution.

All primary analyses will be modified intent-to-treat (M-ITT), such that the groups being compared will be all patients who are randomized and who undergo surgery. Analyses of the safety outcomes in Aims 1 and 2 will be noninferiority assessments, and so 1-tailed. All tertiary analyses will be 2-tailed tests for superiority. Conclusions about the effect of HES will be confirmatory for the primary outcome (urinary NGAL) and more exploratory for other outcomes. We will also conduct a “per protocol” analysis for the primary outcome and describe whether these results differ from the modified intent-to-treat results. In the per-protocol analysis we will analyze patients according to the treatment received as oppose to the randomized treatment, and only those patients who complete the entire trial according to the protocol will be included. In case of a discrepancy, the M-ITT results will be primary.

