Continuous outcomes measured over time (Primary and secondary aims). For the primary outcome (urinary NGAL) and each of the secondary continuous outcomes which are measured over time (e.g., at baseline, within one hour of arrival to ICU following surgery, and 24 hours following completion of surgery), we will assess the treatment effect of HES 130/0.4 versus standard care using linear mixed effects models (with patient as random effect), adjusting for the baseline value of the outcome and any baseline variables for which balance among the randomized groups was not achieved through randomization. We will adjust for the baseline value of the outcome for efficiency, i.e., to obtain a smaller standard error for the estimate of treatment effect to the extent that the baseline value is correlated with the later time points, regardless of baseline balance. An unstructured within-subject correlation structure will be employed, estimating a distinct correlation parameter for each pair of post-baseline measurement times.

If the treatment group-by-time interaction is significant ($P < 0.15$), the treatment effect for a particular outcome will be assessed at each of the post-baseline time points measured, using a Bonferroni (or other appropriate) correction for multiple comparisons procedure if comparing groups at specific time points. Similarly, correction to the significance criterion will be made in all analyses below when comparing multiple times, as appropriate.

Ordinal outcome. Groups will be compared on the ordinal outcome of the RIFLE criteria (Secondary Aim 1) using proportional odds logistic regression, adjusting for baseline imbalance

as needed. We will assess noninferiority using the approach described above for the primary outcome, where $\hat{\beta}_1$ is the estimated treatment effect in the form of a log-odds ratio.

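### The baseline-balance index is defined with the outcome's SD as divisor, which is wrong as written and inconsistent with the plan's own 0.39 benchmark; a minor wording correction is needed.

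*Combined protocol and SAP*

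**What the plan says.** The rule stands in the combined protocol and SAP, in the opening paragraph of STATISTICAL METHODS. The two groups are compared on "potentially confounding baseline variables (including duration of cardiopulmonary bypass, use of anti-fibrinolytic therapy, preoperative anticoagulant medications, including clopidogrel" and similar items, so the list mixes a duration with proportions. The index is the "observed difference in means or proportions divided by the pooled standard deviation of the outcome". A variable for which it "is greater than 0.25 will be considered imbalanced and adjusted for as a covariate in each of the below analyses".

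A bracketed note then defends the threshold: "A standardized difference of 0.25 is conservative (should be 0.39"), "based on the expected 2.5th and 97.5th percentiles of the sampling distribution", computed as 1.96 × sqrt(2/n) with n "per group = 50 = 0.39".

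The result is used further on. Under the heading on continuous outcomes measured over time, the mixed models are specified as "adjusting for the baseline value of the outcome and any baseline variables for which balance among the randomized groups was not achieved through randomization". The paragraphs on ordinal, time-to-event and binary outcomes also call for adjustment for baseline imbalance. None of them restates or changes the divisor, so the opening paragraph is its only definition.

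**The concern.** A standardized difference is free of units because a variable's group difference is divided by that same variable's SD. Dividing minutes of bypass, or a proportion on clopidogrel, by the SD of urinary NGAL does not do this. The result changes with the unit of the baseline variable, with the outcome chosen, and with whether that outcome is analysed raw or logged. For ordinal RIFLE categories, binary morbidity or censored durations, it is unclear what SD would be used at all. A single list of covariates meant for all analyses could become a different list for each outcome.

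This matters because the sentence is an operative rule. It helps to fix the covariates of the confirmatory noninferiority model for NGAL. The EXECUTIVE COMMITTEE section says the interim analyses will be programmed in advance, so the wording may well be turned into code. Two statisticians could read it differently and arrive at different primary models.

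The point concerns the formula only, not the value 0.25 or the choice to select covariates from the data.

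**Working it through.** **1. Reproduce the plan's figure.** With n = 50 per group, 1.96 × sqrt(2/50) = 1.96 × 0.200 = 0.392, which agrees with the stated 0.39.

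**2. See which divisor this implies.** Let s be the SD of the baseline variable and D the divisor. With no true imbalance, the difference in means has standard error s × sqrt(2/n). The 95% limit of the index is therefore 1.96 × sqrt(2/n) × s/D. It equals 0.392 for every variable only if D = s. With D an outcome SD, the limit is 0.392 × s/D, which has no single value. The definition and the benchmark in the same paragraph cannot both stand.

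**3. Inputs for an illustration.**
- n = 65 per group, from the maximum of 130 patients (Interim monitoring analyses; Sample size calculations).
- Log-NGAL SD from the assumed CV of 25% (Sample size calculations): sqrt(ln(1 + 0.25²)) = 0.246.
- Log-NGAL SD from the quoted quartiles 13.5 and 82.9 in the same section: ln(82.9/13.5)/1.349 = 1.345.
- Raw NGAL SD from those quartiles and the median of 28.3, taken as lognormal: 28.3 × exp(1.345²/2) × sqrt(exp(1.345²) − 1) ≈ 158.
- Bypass-time SD: not in the documents. I assume 30 min and show 15 to 60 min.

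**4. Chance that a balanced variable is flagged.** P = 2 × [1 − Φ(0.25 × D/(s × sqrt(2/65)))], with sqrt(2/65) = 0.1754.
- D = s: 0.25/0.1754 = 1.425, so P = 15.4% whatever the units.
- D = 0.246, s = 30 min: 0.0616/5.262 = 0.0117, so P = 99.1%.
- D = 158, s = 30 min: 39.5/5.262 = 7.5, so P ≈ 0.

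| Bypass-time SD | own SD | D = 0.246 | D = 1.345 | D = 158 |
|---|---|---|---|---|
| 15 min | 15.4% | 98.1% | 89.8% | about 0% |
| 30 min | 15.4% | 99.1% | 94.9% | about 0% |
| 60 min | 15.4% | 99.5% | 97.5% | 0.02% |
| 30 min, recorded as 0.5 h | 15.4% | 48.3% | 0.01% | about 0% |

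The last row is the second row with the unit changed. At D = 0.246, recording hours instead of minutes moves the chance from 99.1% to 48.3%.

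**5. Binary variables.** The gap in proportions needed to exceed 0.25 is 0.25 × D:
- D = 0.246: 0.062, about 6 percentage points.
- D = 1.345: 0.336, about 34 points.
- D = 158: 39.5, which a proportion cannot reach.

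As an assumed example, take clopidogrel use of 10% against 30%. Its own pooled SD is sqrt((0.10 × 0.90 + 0.30 × 0.70)/2) = 0.387, so the proper index is 0.20/0.387 = 0.52 and the variable is flagged. Literally, it scores 0.20/0.246 = 0.81 (flagged), 0.20/1.345 = 0.15 (missed) or 0.20/158 = 0.001 (missed).

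**The case against.** The strongest reply is that this is a slip of wording which its own paragraph resolves. The index is called standardized and is recommended as a measure of balance. The 0.39 limit works only with the variable's own SD. One covariate list is meant to serve all analyses. The reference attached to the note is, by its title, about balance diagnostics for baseline covariates. On this view the word for outcome loosely means the variable being compared, and a competent programmer would use the usual index. I accept this as the probable intention. It does not remove the error, because the only explicit definition in the plan says something else.

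A reader might go further and infer that the rule selects the wrong covariates in every model. The documents do not support that. The harm arises only if the sentence is applied literally, and even then some of the right variables could be picked. A reader might also infer that the literal rule can never admit a binary variable. That depends on the outcome's scale: it is true at a raw SD of 158 but false at a log SD of 0.246, where a gap of about 6 points suffices.

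The plan also contains safeguards. The models for repeated continuous outcomes include the outcome's baseline level whether or not it is balanced. The Sensitivity analyses paragraph adjusts the primary outcome for bypass time, length of surgery and hypothermia whatever the rule flags. These safeguards stand, though they do not reach clopidogrel or antifibrinolytic use, and the sensitivity analysis does not extend to the secondary outcomes. Finally, the arithmetic above gives flagging frequencies only. It shows no effect on the NGAL estimate, its standard error, the type I error or the noninferiority conclusion.

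**Conclusion.** The concern holds as a minor correction. The divisor is wrong as written and contradicts the benchmark in the same paragraph, and nothing elsewhere in the plan corrects it. Read literally, the chance of flagging a balanced bypass time runs from about 0% to about 99% according to the NGAL SD used, against 15.4% with the proper divisor at 65 per group. The 99% figure rests on an assumed bypass-time SD of 30 min, but the contrast persists from 15 to 60 min. The contradiction with 0.39 needs no assumption beyond the plan's own formula.

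The practical impact is limited, because the intended meaning can be recovered from the paragraph and because of the safeguards in the models and the sensitivity analysis.

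**What to change.** In the opening paragraph of STATISTICAL METHODS, change the divisor to the pooled standard deviation of that baseline variable. For a proportion, define it as the square root of the average of p(1 − p) over the two groups. State that the absolute value of the index is compared with 0.25. Each variable then has one value that serves all analyses, and the 0.39 benchmark follows from the definition.

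The cost is one amended sentence. The 0.25 threshold, the sample size and the data collection are unchanged. Any analysis code already written should be checked against the amended definition.

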Interim monitoring analyses. We will conduct interim analyses for the parameter urinary NGAL (assessing safety [i.e., noninferiority] and non-safety [i.e., noninferiority not found]) at every 1/6th (16.7%) of the maximum enrollment of 130 patients, or approximately at every 22 or 23 patients, in a group sequential design. We will use the gamma spending function with gamma of -5 for safety (alpha spending; very conservative, like O-Brien-Fleming boundaries) and gamma of 0 for futility, or non-safety (beta spending; fairly aggressive, like Pocock boundaries). We spend the beta faster than the alpha in order to be able to detect any potential harm of the treatment as early as possible in the trial. Table 3 gives the P-value boundaries for efficacy and futility at each interim look (columns 5 and 6). Column 2 gives the total sample size at each look. The last 2 columns give the probability of crossing a boundary when the null hypothesis is true (Under H0) and when the alternative (noninferiority) is true (H1). For example, if Voluven is truly noninferior, the probability of crossing the safety boundary is 3.1% at the first look, $3.1\% + 12.7\% = 16\%$ through the second look, and so on. The below figure displays the boundaries on the z-scale (A) and the error spending functions (B) for this design.

Table 3. Interim Monitoring -- Group Sequential Design Boundaries							
Information action	Cumulative Accrual	Alpha Spent	Beta Spent	P-value Boundaries		Boundary Crossing Probabilities	
				Safety H0	Non-safety H1	Under H0 For nonsafety	Under H1 For safety
0.167	22	0.0004	0.017	<0.001	0.746	0.254	0.031
0.333	43	0.001	0.033	0.001	0.471	0.303	0.127
0.500	65	0.003	0.050	0.002	0.256	0.217	0.229
0.667	86	0.006	0.067	0.005	0.125	0.122	0.252
0.833	108	0.013	0.083	0.010	0.056	0.060	0.183
1.000	130	0.025	0.100	0.021	0.021	0.025	0.078

A. Z-statistic Stopping boundaries

B. Alpha and beta spending functions

Sample size calculations (Aim 1):

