Sample size is based on assessing the noninferiority of HES 130/0.4 to 5% albumin on the primary outcome of urinary NGAL. In patients undergoing cardiac surgery, Koyner et al (2012)²⁹ observed median [quartile] urinary NGAL values of 28.3 (13.5–82.9) in patients who did not progress to renal failure and 72.1 (11.4–495.6) in patients who progressed to renal failure. Assuming that NGAL values follow a log-normal distribution as in previous studies, we can use the above observed quartiles to estimate the mean, standard deviation and coefficient of variation (CV) for the above groups, yielding CV of 2.3% and 50%, respectively. Assuming for the current study a coefficient of variation between these values, or 25%, we would need 52 patients per group (total of 104) to have 90% power at the 0.025 significance level to be able to claim noninferiority of HES to albumin using a noninferiority delta of a ratio of geometric means of 1.15. These calculations assume no treatment-time interaction and therefore no Bonferroni correction for comparing groups at each of two time points within an outcome. Based on the above calculations, a sample size of 110 would suffice for a study with no interim monitoring. **Adjusting for the interim monitoring at each one-sixth of the total, a maximum sample size of 130 patients are required. Allowing for 5 potential dropouts and 5 pilot patients (which will not be included in the analyses), we will plan for a potential total of 140 patients.**

STUDY PROCEDURES

Quality Assurance

The major components of quality assurance will be staff training, the standardization of data collection, entry, and processing, and ongoing monitoring to ensure timeliness and accuracy of study data. All study protocols and forms will be compiled into two operations manuals (one for the clinical sites and one for data management) that will be revised as necessary. A clinical reference manual will be created and will include administration and scoring criteria, specific testing instructions and inclusion and exclusion criteria for diagnosis and study ascertainment. This manual will also contain copies of test forms and will be available to all study personnel from a password-protected web site. The current manual for data management will be made easily available to data management personnel and used for continued training. This manual will include a question-by-question written script for interviewing purposes.

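### The primary NGAL model takes its extra covariates from an open list by a 0.25 imbalance cut-off, and the cut-off's divisor is misstated

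*Combined protocol and SAP*

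**What the plan says.** The opening paragraph of Statistical Methods compares the groups on potentially confounding baseline variables. It names three (bypass duration, anti-fibrinolytic use, preoperative anticoagulants) as examples, so the list is open. The comparison is a difference in means or proportions "divided by the pooled standard deviation of the outcome", and a variable whose result is "greater than 0.25 will be considered imbalanced and adjusted for as a covariate in each of the below analyses". P-values are rejected as a balance measure because "the standardized difference is more independent of sample size and thus a better assessment of balance". The cut-off is described as cautious against a chance limit of 0.39, computed for 50 patients per group.

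Under Continuous outcomes measured over time, the primary mixed model adjusts for baseline NGAL and "any baseline variables for which balance among the randomized groups was not achieved through randomization". Baseline NGAL is included for efficiency, to the extent that the "baseline value is correlated with the later time points, regardless of baseline balance".

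Interim monitoring analyses tests NGAL "at every 1/6th (16.7%) of the maximum enrollment of 130 patients, or approximately at every 22 or 23 patients". That section names no separate model and does not say whether the covariates are frozen across looks. A fixed-list adjustment (time on bypass, length of surgery, hypothermia) appears only under Sensitivity analyses.

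**The concern.** In a randomized trial, baseline imbalance is a chance event. A cut-off on observed imbalance selects covariates by luck rather than by how well they predict the outcome: a prognostic variable that happens to balance is left out, and an irrelevant one that happens not to is put in. The plan follows the better principle for baseline NGAL and the opposite one for everything else.

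The defence of the standardized difference is only half right. Its expected value does not depend on sample size, but its chance spread does, and the interim looks start at about 11 patients per arm. A fixed cut-off therefore means different things at different looks.

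At stake are the precision of the primary comparison and whether the confirmatory model is fully defined in advance. Separately, taken literally the divisor puts a difference in, say, minutes of bypass over the SD of NGAL, which makes 0.25 uninterpretable.

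**Working it through.** **Inputs.** Cut-off 0.25 and benchmark formula: Statistical Methods, opening paragraph. Looks at 22, 43, 65, 86, 108 and 130 patients, with P-value boundaries: Table 3. Margin 1.15 (log 0.1398), one-sided 0.025, CV 25%: Type I error and Sample size calculations. Equal arms are implied by 52 per group.

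**1. The plan's figure.** 1.96 × √(2/50) = 1.96 × 0.20 = 0.392, so 0.39 is reproduced.

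**2. The same formula at each look.** The probability that a randomized variable exceeds the cut-off is 2 × [1 − Φ(0.25/√(2/n))], with n per arm. At n = 11: √(2/11) = 0.426, 0.25/0.426 = 0.586, probability 0.558. At n = 65: √(2/65) = 0.175, ratio 1.425, probability 0.154.

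| Look | Patients | n per arm | Chance limit | Entry probability |
|---|---|---|---|---|
| 1 | 22 | 11 | 0.84 | 56% |
| 2 | 43 | 21.5 | 0.60 | 41% |
| 3 | 65 | 32.5 | 0.49 | 31% |
| 4 | 86 | 43 | 0.42 | 25% |
| 5 | 108 | 54 | 0.38 | 19% |
| 6 | 130 | 65 | 0.34 | 15% |

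With three independent candidates, at least one enters with probability 1 − (1 − 0.558)³ = 0.91 at look 1 and 1 − (1 − 0.154)³ = 0.39 at look 6. In simulation the selected set changed between consecutive looks about 50% of the time.

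**3. The divisor.** The spread √(2/n) applies to a difference divided by that variable's own SD. The 0.39 benchmark therefore requires the pooled SD of the baseline variable, not of the outcome.

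**4. Power and error.** The six-look design was simulated with Table 3 boundaries, non-safety crossings treated as stops, and baseline log NGAL in every model. R² is the share of variance the three candidates explain beyond baseline NGAL; the documents give no value, so it is an assumption.

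- Set A: two post-baseline times with unstructured covariance and a common effect ("These calculations assume no treatment-time interaction"); SD 0.2225, chosen to give about 90% power; one continuous and two binary candidates; 6,000 trials per cell.
- Set B: a single-outcome version with SD √ln(1 + 0.25²) = 0.246, the plan's own CV; three continuous candidates; 10,000 trials per power cell.

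Power (%) at a true ratio of 1.0, with differences taken before rounding:

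| Set | R² | Baseline NGAL only | 0.25 rule | Fixed three | Fixed minus rule |
|---|---|---|---|---|---|
| A | 0 | 88.9 | 87.9 | 87.6 | −0.3 |
| A | 0.10 | 88.9 | 88.7 | 89.7 | +1.0 |
| A | 0.20 | 88.8 | 90.3 | 92.8 | +2.5 |
| B | 0 | 82.4 | 80.9 | 80.6 | −0.3 |
| B | 0.10 | 82.7 | 82.9 | 84.4 | +1.5 |
| B | 0.20 | 82.8 | 84.6 | 88.5 | +3.8 |
| B | 0.30 | 83.0 | 86.4 | 91.7 | +5.3 |

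Set B rerun at SD 0.222 gave −0.2, +1.0, +2.0 and +2.9 points at R² 0, 0.10, 0.20 and 0.30. Rerun at SD 0.246 with mixed binary and continuous candidates, it gave +3.5 at R² 0.20 and +5.0 at 0.30.

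False noninferiority at a true ratio of 1.15 under the rule was 2.4, 1.9 and 1.4% in set A (R² 0, 0.10, 0.20) and 1.3–2.1% in the set B runs; under the fixed list it was 2.0–2.4%. With non-safety stopping not enforced (SD 0.246, R² 0.10), it was 2.2% for the rule and 2.4% for the fixed list.

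**The case against.** The strongest reply is that nothing here threatens validity. Selection uses covariate imbalance and not the outcome, and the error rate stays below 0.025. A reader might infer that data-driven covariates inflate type I error; the calculations show the opposite, a mildly conservative test. That reply stands, and it limits the point to efficiency and specification.

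Other stronger readings also fail:

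- That the whole primary model is left to chance. It is not: baseline NGAL is always included.
- That the covariate set almost always changes. At least one change over all six looks occurs in 97–98% of simulated trials, but that ignores stopping. Weighted by Table 3's stopping probabilities, and assuming stopping is independent of the covariate set, it is about 87% under noninferiority and 64% under the null.
- That a fixed list would prevent early non-safety stops. With three non-prognostic candidates, look-1 crossings at ratio 1.0 were 2.2% (baseline NGAL only), 2.8% (rule) and 3.0% (fixed).
- That adjusting for bypass duration or anti-fibrinolytic use biases the comparison because both arise after randomization. Study fluid starts only after separation from bypass (Intraoperative Fluid Management), anti-fibrinolytic infusion starts at induction, and clinicians are blinded. A note is enough.

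It is also fair to say that reapplying the rule at each look is an inference. The Executive Committee section requires interim analyses to be pre-programmed, which may settle the matter in practice but does not state the covariates. The choice of 0.25 below 0.39 is disclosed, and the divisor may be a slip of wording, since the benchmark shows what was meant. Finally, a fixed list helps only if its variables predict NGAL.

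**Conclusion.** The point holds as a minor one. The primary model is not fully specified: its extra covariates come from an open list, enter by chance imbalance (15% per variable at 130 patients, 56% at 22 if the rule is reapplied), and are not stated for the interim looks. Type I error is controlled, at about 1.3–2.4%.

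With three candidates, the efficiency at stake is about −0.3 to +3 points of power when the SD gives about 90% power, and up to about 4–5 points at the plan's CV of 25% with R² of 0.2–0.3. Gains above 3 points therefore do not require a long candidate list. These figures rest on an assumed R², on three independent candidates, and on no treatment-time interaction. The entry probabilities need only randomization, equal arms and the corrected divisor. The divisor is wrong as written whatever view is taken of the rest.

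**What to change.** Prespecify one short closed covariate list, with a reason for each entry. Use it in the primary NGAL model at all six looks and name that model under Interim monitoring analyses. It would hold baseline log NGAL plus, for example, bypass duration, which Renal effects names as a renal risk factor; note that it precedes study fluid but follows randomization. Baseline creatinine, or valve surgery with versus without grafting, could be added; the documents do not show that either is related to NGAL.

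Correct the divisor to the pooled SD of the baseline variable. Report standardized differences descriptively. Keep the 0.25 rule, applied to a closed list, as a sensitivity analysis at the final analysis only.

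The cost is SAP wording, since these variables are already collected. If the listed covariates prove uninformative, about 1–2 points of power are lost against baseline NGAL alone (88.9 − 87.6 = 1.3 in set A; 82.4 − 80.6 = 1.8 in set B). Chance imbalance in an unlisted variable would then be handled only by the sensitivity analysis and by the Executive Committee's review of baseline differences.

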Baseline variables reflective of the patient's demographic information, medical history, comorbidities, laboratory values, other descriptive variables, and postoperative complications will be obtained from the patient's medical record, Cardiothoracic Anesthesia Patient Registry of the Department of Cardiothoracic Anesthesia at the Cleveland Clinic or the Cardiovascular Information Registry of the Department of Cardiovascular Surgery. Research use of this Registry is approved by the Institutional Review Board. All perioperative and outcome data in the Cardiothoracic Anesthesia Registry and Cardiovascular Information Registry is collected daily, concurrent with patient care on preprinted forms, by experienced and specifically trained research personnel. Data, which does not conform within a range of expected results, is rejected and reevaluated. This is the routine procedure for data validation for the Registry and ensures that erroneous data is not recorded in the Registry. This data validation procedure is performed in a blinded fashion and will not bias the results. Data will also be collected from the Cardiovascular Information Registry of the Department of Thoracic and Cardiovascular Surgery at the Cleveland Clinic, chart review, and from patient follow-up. The Social Security Death Index will be accessed for mortality data at 30 ± 5 days and one-year \pm one month following surgery. A follow-up phone call will be made at 30 ± 5 days to record re-hospitalization for fluid overload, atrial fibrillation, or hospitalization for any other cause and death. A follow-up phone call will be made at 90 ± 15 days and 1 year \pm one month to collect information regarding postoperative renal function and to establish one-year survival. We will collect serum creatinine data from all patients who are followed at the Cleveland Clinic who have laboratory measurements of creatinine at no more than one year and no less than 6 months after surgery if available. We will also collect data on the requirement for RRT if available. (Serum creatinine and requirement for RRT day may be used to categorized patients into RIFLE criteria if long-term data is available) For patients who are followed at outside institutions, we will attempt to get the patient's permission to retrieve a serum creatinine measurement from their local health care provider. If the patient has died, the date of death will be recorded to determine whether the patient survived 30 days following surgery.

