Type I error. The significance level will be 0.025 for the 1-tailed noninferiority tests for the primary outcome and for each set of the secondary outcomes, and 0.05 for each of the 2-tailed superiority tests for tertiary outcomes (i.e., no adjustment for multiple testing for tertiary outcomes).

Our primary hypothesis is that HES 130/0.4 is noninferior to standard care effects on **mean urinary NGAL** measured within one hour of arrival to ICU and 24 following completion of surgery. We a priori define the noninferiority delta for urinary NGAL as a ratio of geometric means (since NGAL data are expected to be lognormal) of 1.15, for an effective delta of 15% of the control group mean. [Note: for this and other outcomes, if the data are non-normal, a log-transformation will be attempted and the treatment effect (if normal on the log-scale) will be summarized as the ratio of geometric means, equivalent to the difference in means of the log-transformed data.] As noted below under “Continuous outcomes measured over time (Primary and Secondary Aims)”, we will assess the treatment effect for the primary outcome in the context of a linear mixed model which allows us to simultaneously assess the effect across the collapsed time points if there is no group-time interaction, or else at specific times if there is an interaction detected. We will conduct tests for noninferiority using treatment effect estimates from the linear mixed model and applying 1-tailed t-tests for noninferiority as described in Mascha and Sessler (2011) [Mascha EJ, Sessler DI: Statistical grand rounds: Equivalence and noninferiority testing for regression models and repeated measures designs. Anesth Analg 2011; 112: 678–87], and with t-statistic as follows:

$$T_{NI} = \frac{\hat{\beta}_1 + \delta}{SE_{\hat{\beta}_1}}, \text{ where } \hat{\beta}_1 \text{ is the estimated treatment effect with standard error}$$

$SE_{\hat{\beta}_1}$ and noninferiority delta of δ .

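### The per-protocol NGAL analysis keeps only patients who complete an undefined entire trial and groups them by treatment received; it should be defined by events up to the 24-hour sample and analysed as randomized

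*Combined protocol and SAP*

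**What the plan says.** The analysis-population paragraph of STATISTICAL METHODS makes modified intent-to-treat (M-ITT) the primary approach: "the groups being compared will be all patients who are randomized and who undergo surgery". It then adds a supportive analysis: "We will also conduct a “per protocol” analysis for the primary outcome and describe whether these results differ" from the M-ITT results. Two rules define that analysis. On grouping, "we will analyze patients according to the treatment received as oppose to the randomized treatment". On membership, "only those patients who complete the entire trial according to the protocol will be included". The paragraph closes with an order of precedence: "In case of a discrepancy, the M-ITT results will be primary".

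The primary outcome is early. The Type I error paragraph describes mean urinary NGAL "measured within one hour of arrival to ICU and 24 following completion of surgery", and the later sample may be taken sooner if the patient leaves the ICU before 24 hours.

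The trial goes on much longer. Under Perioperative Data collection there are calls at 30 days, 90 days and one year, the last two "to collect information regarding postoperative renal function and to establish one-year survival". Table 2 has a one-year column. The Patient withdrawal section lets a patient leave treatment only, or both treatment and follow-up. No section says at what point a patient counts as having completed the trial.

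**The concern.** A per-protocol set for a 24-hour outcome should depend on what happened up to that sample. Here membership can depend on events weeks or months later. The section justifying the kidney markers says that postoperative NGAL correlates with severity and duration of kidney injury, need for renal replacement therapy, and mortality. Later death is therefore related to the value being analysed. If HES harmed kidneys and more of the affected HES patients later died or left follow-up, they would drop out of the comparison and the HES mean would look better than it was.

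This matters in a noninferiority trial because M-ITT keeps patients whatever their exposure or adherence, which can pull the arms together. The other planned sensitivity analyses deal with missing data and with bypass time, length of surgery and hypothermia. Only the per-protocol analysis looks at adherence, so it should not carry a selection effect that can act in the same direction.

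The grouping rule adds a second problem. A patient given the other arm's solution is to be regrouped under one clause and, as a protocol departure, excluded under the next.

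**Working it through.** The plan gives no size, power or exclusion rate for the per-protocol set, so there is no figure of its own to reproduce. The check has two parts.

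**1. The text, side by side**

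- Outcome window: ICU arrival and about 24 hours after surgery.
- Scheduled contacts: 30 days, 90 days and one year.
- Follow-up counts as part of participation, since a patient can withdraw from it.
- The completion rule has no time point.

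On a literal reading, death or withdrawal from follow-up after the 24-hour sample can remove a patient whose NGAL data are complete. A missing late creatinine is a weaker case. Late creatinine and renal replacement data are collected only where available, so their absence need not be a protocol departure.

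**2. What such exclusions could do (all exclusion inputs assumed)**

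*Illustration A.* Let a share h of HES patients have NGAL multiplied by 3, with no such effect under albumin and no selective exclusion there. The ratio of geometric means is exp(h ln 3). If a fraction q of the harmed patients is excluded, the share becomes h' = (1 − q)h / (1 − qh), and the ratio becomes exp(h' ln 3). With h = 0.10:

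| q | h' | Ratio |
|---|---|---|
| 0 | 0.100 | 1.116 |
| 0.10 | 0.09/0.99 = 0.0909 | 1.105 |
| 0.20 | 0.08/0.98 = 0.0816 | 1.094 |
| 0.50 | 0.05/0.95 = 0.0526 | 1.060 |

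*Illustration B.* Let fH and fC be the shares excluded from the HES and albumin arms, and let R be the NGAL geometric-mean ratio of excluded to retained patients, the same in both arms. The retained log mean is the full log mean minus f ln R, so the estimated ratio is multiplied by exp[−(fH − fC) ln R].

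- fH = fC = 0.05: the multiplier is 1, so there is no bias at any R.
- fH = 0.10, fC = 0.05, R = 1.5: exp(−0.05 × 0.405) = 0.980.
- fH = 0.10, fC = 0.05, R = 2.55: exp(−0.05 × 0.935) = 0.954.

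R = 2.55 is 72.1/28.3, the two medians in the sample size section, used here only as an upper assumption.

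Now suppose the true ratio equals the margin of 1.15, with 65 patients per arm (half of 130), a one-sided 0.025 test and interim looks ignored. The chance that the per-protocol test would nevertheless show noninferiority is Φ(−bias/SE − 1.96), where bias = −(fH − fC) ln R and SE = SD × √[1/(65(1 − fH)) + 1/(65(1 − fC))]. For 10% versus 5% excluded and R from 1.5 to 2.55:

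- SD 0.246, from the planned 25% CV, √ln(1 + 0.25²): 0.066 to 0.179.
- SD 1.345, from the quartiles 13.5 and 82.9, ln(82.9/13.5)/(2 × 0.6745): 0.030 to 0.038.

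This scenario removes 0.10 × 65 + 0.05 × 65 = 9.75, or about 10 patients. The plan allows for 5 dropouts and does not tie that allowance to the per-protocol set.

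**The case against.** The strongest reply is that the sentence describes an analysis for the primary outcome, so its authors may have meant completing the intervention and the 24-hour sampling. Deaths at the follow-up points are themselves collected outcomes and can come from a death index. On that view, a patient who dies has not clearly failed to complete the protocol. This stands as a possible reading. A reader might infer that the plan requires completion to one year, but it does not say so: one year comes from putting an undefined term beside the follow-up schedule. What remains is that the literal wording permits the exclusion and nothing rules it out.

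A second reply is that crossovers have departed from the protocol and would be excluded anyway, so received and assigned solution coincide among those retained. That is largely right. A reader might infer that regrouping breaks randomization on a meaningful scale; the text supports only that the two clauses conflict. Pharmacy repackaging and coding should also keep crossovers few.

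Third, the protocol's correlation concerns kidney injury, renal replacement therapy and mortality. It does not cover patients lost to a telephone call, so it cannot be said that excluded patients in general have the highest NGAL. This also stands. Losing half of the harmed patients, the lower end of Illustration A, is an extreme case for an elective population that excludes critical illness and creatinine above 1.6 mg/dL.

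**Conclusion.** The point holds as a defect in the definition of a supportive analysis. As worded, a 24-hour comparison can be conditioned on later events, some of which the protocol links to NGAL, and a crossover is both regrouped and excluded.

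Bias arises only if exclusion differs by arm, in rate or in its relation to NGAL. It could then run toward noninferiority, as in both illustrations, or away from it if the imbalance is reversed. Its size cannot be derived from the documents. Under Illustration A, 1.12 falls to between 1.105 and 1.06 across 10% to 50% exclusion of harmed patients, with the small end more plausible. Under Illustration B, the effect on error depends heavily on whether the planned 25% CV or the much wider spread implied by the quoted quartiles applies.

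A reader might infer that the trial's noninferiority conclusion is at risk. The documents do not support that: M-ITT is primary, includes every randomized patient who has surgery, and prevails if the two analyses differ. What is weakened is the value of the per-protocol result as corroboration. Leaving completion undefined also allows the set to be settled after results are known.

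**What to change.** Replace the two per-protocol rules with a definition that uses nothing after the 24-hour NGAL sample. The set would be patients who were randomized, had surgery, received the assigned study solution and none of the other arm's, had no major protocol deviation before the sample (with the list of major deviations fixed before unblinding), and have post-baseline NGAL available. Analyse them by randomized group, with crossovers excluded. If an analysis by solution received is still wanted, specify it separately and label it as-treated. Report the number excluded, with reasons, by arm. Leave the M-ITT precedence rule as it is.

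The cost is a few lines of SAP wording. No extra data, visits or patients are needed.
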